4.0 STUDY DESIGN

The single-site study design is a 4-year, randomized, two-group, attention-controlled clinical trial. Women (N=250) will be screened for childhood adversity, enrolled in pregnancy to obtain baseline OXT data. Soon after birth (pre-hospital discharge), M-I dyads who continue to be eligible are randomized into the intervention group ($n=125$) and taught to administer the ATVV intervention daily for 3 months or randomized into the attention control group ($n=125$) and taught safe infant care. There are a total of 5 study visits (3rd trimester, soon after birth, 1st postnatal month, 2nd postnatal month, 3rd postnatal month), plus a follow-up phone call at 6 postnatal months to assess quality of parenting using a self-report questionnaire.

This is a randomized controlled trial (RCT) comparing data between the ATVV and Attention Control groups. Random assignment is centrally controlled by our statistician using a computer-generated list of random numbers (0=intervention and 1=control), balanced so that half the M-I dyads are in the ATVV group. Mothers will be asked to not disclose their group assignment to mothers in the postnatal unit.

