4.1.5 Screen Failures

If a mother scores less than 2 on the ACE, we will remove all 13 elements of identification and retain only the ACE score without the corresponding answers to the 10 questions. We would like to determine if the inclusion/exclusion criteria such as the requirement to have access to a cell phone, screens out any portion of the population with high ACE scores. Additionally, this study has a second level of screening which occurs at the birth of the baby. If a participant delivers a baby not meeting the inclusion criteria such as full term (37 weeks 0/7 days) and healthy, they are withdrawn from the study and are not randomized. A minimal set of screen failure information is required to ensure transparent reporting of screen failure participants, to meet the Consolidated Standards of Reporting Trials (CONSORT) publishing requirements and to respond to queries from regulatory authorities. Minimal information includes demography, screen failure details, eligibility criteria, and any serious adverse event (SAE) which are retained with study records. Because there are no modifiable factors associated with screen failure, we do not rescreen participants.

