4.8.1 Evaluate Efficacy of ATVV

Aim 1: Evaluate the efficacy of daily ATVV among mothers with childhood adversity on behavioral and physical measures of M-I synchrony in a randomized study with an Attention Control group. The goal of our analysis is to determine treatment arm differences at the study endpoint (3 postnatal months), using a 2.5% type I error rate and two-sided test for our primary outcomes. We will use 5% type I error rate and Benjamini Hochberg correction among related groups of secondary outcomes.⁽¹⁴⁷⁾ We will estimate treatment effects with and without key covariates known to be associated with M-I synchrony (e.g., mental health, adversity, infant feeding method, infant health status, and 1-month Parenting Stress Index) which will increase the power of the test. For infant outcomes, we will include sex as a covariate and test for treatment effect differences by sex using an interaction term. Our statistical method for the physical measures, measured at baseline (late pregnancy) and monthly intervals (1-, 2-, and 3- postnatal months), will be MMRM regressing the outcome on indicators for treatment, time, and their interaction. For the physical measures the goal is to determine treatment arm differences in change from baseline to the study endpoint. In contrast, our method for the behavioral outcomes, measured once at the study endpoint, will be a general linear model regressing the outcome on an indicator for treatment arm. We will conduct intention to treat (ITT) and per protocol analyses (defined as completing 80% or more of daily ATVV sessions) and compare our findings. While missing data will be minimized through careful procedures, some missing data are inevitable with longitudinal studies. In order to retain all randomized participants for ITT, we will use multiple imputation to predict missing outcomes with all available measures, and model aggregated results across imputation datasets.⁽¹³⁸⁾ For physical measures where we have repeated measurements, we will compare multiple imputation results to the full information maximum likelihood approach available through MMRM. We will use inclusive models with auxiliary variables related to missingness, among covariates collected at baseline, if needed to support the missing at random assumption.^(138, 139) Sensitivity analyses will assess the robustness of our findings if we find imbalanced baseline characteristics in spite of randomization, characteristics associated with attrition, or non-ignorable missing data. We will conduct fidelity and dose response analyses in addition to our main effects models. Dose (frequency of ATVV sessions) will be collected daily for three months from the treatment arm participants and can be used to explore the patterns of adherence over time as well as optimal dose associated with OXT system changes by month.

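### The oxytocin MMRM leaves the pre-randomization baseline free to differ by arm, which can cost precision (size unknown), and its change-from-baseline target does not exempt infant saliva, which has no baseline

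*Combined protocol and SAP*

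**What the plan says.** Section 4.8.1 describes the physical (oxytocin-system) measures as "measured at baseline (late pregnancy) and monthly intervals" after birth. Their analysis "will be MMRM regressing the outcome on indicators for treatment, time, and their interaction", and for them "the goal is to determine treatment arm differences in change from baseline to the study endpoint". Effects are to be estimated with and without key covariates. Those covariates are given as examples, and the marker's own baseline value is not among them. For ITT, "we will use multiple imputation to predict missing outcomes with all available measures", and the multiple-imputation results for the repeated measures are compared with the likelihood-based MMRM.

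Section 4.0 has women "enrolled in pregnancy to obtain baseline OXT data"; then, soon after birth, "M-I dyads who continue to be eligible are randomized into the intervention group".

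The Schedule of Events (1.4) marks maternal blood at baseline, T1, T2 and T3, but infant saliva at T1, T2 and T3 only. Aim 1 H1 (section 3.2) names both the maternal markers and infant salivary oxytocin at all three postnatal months. Section 4.8.1 also states a general Aim 1 goal: "The goal of our analysis is to determine treatment arm differences at the study endpoint (3 postnatal months").

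**The concern.** With baseline as a response visit and a full treatment-by-time structure, the model has a free arm difference at baseline. Randomization after the baseline draw makes the true value of that difference zero among randomized dyads. The change contrast subtracts a noisy estimate of it.

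Validity is not in question. The change contrast and the month-3 arm difference have the same expected value. What is at stake is precision for the maternal markers, which are secondary outcomes and are also subject to Benjamini-Hochberg correction. H1 names months 1, 2 and 3, and the loss can arise at each.

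Infant saliva is a separate and smaller matter. The change-from-baseline sentence covers the physical measures without exception, yet for saliva the contrast cannot be formed.

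**Working it through.** **The plan's own figure.** Section 4.7 gives 80% power for 0.44 SD in the primary outcomes, with 100 per arm and two-sided alpha 0.025. SE = sqrt(2/100) = 0.1414; 0.44/0.1414 = 3.111; 3.111 - 2.241 = 0.870, which gives 80.8% (80.2% with the t distribution). The figure reproduces. Section 4.7 gives none for the Aim 1 oxytocin tests.

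**Formula, complete data.** Take the month-3 SD as 1, s = baseline SD / month-3 SD, rho = baseline-to-month-3 correlation, and n per arm.

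- Planned change contrast: Var = 2(s² + 1 - 2·rho·s)/n
- Baseline-adjusted or common-baseline estimate (large samples): Var = 2(1 - rho²)/n
- Since s² + 1 - 2·rho·s = (s - rho)² + (1 - rho²), the ratio is 1 + (s - rho)²/(1 - rho²). It is never below 1, and equals 1 only when s = rho.
- With s = 1 the ratio is 2/(1 + rho).

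Example with n = 100, s = 1, rho = 0.5: 2(1 + 1 - 1)/100 = 0.0200 against 2(0.75)/100 = 0.0150, a ratio of 1.33. With 100 per arm at every visit, rho 0.3, 0.5, 0.7, 0.8 and 0.9 give 1.54, 1.33, 1.18, 1.11 and 1.05.

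**With dropout.** The documents give neither rho nor the SDs. Assumptions: 125/117/108/100 per arm at baseline/T1/T2/T3; equal SDs; the same rho from baseline to each postnatal visit; correlation among postnatal visits 0.5 (0.7, 0.8 and 0.9 when rho is 0.7, 0.8 and 0.9). Variances come from the generalized least squares information matrix with known covariance. The planned model has 4 time and 4 treatment terms, and its contrast is treatment at month t minus treatment at baseline. The common-baseline model has 4 time and 3 postnatal treatment terms. The detectable difference at 80% power is (1.960 + 0.842) × SE, two-sided 0.05, before Benjamini-Hochberg, in month-3 SDs (computed from unrounded SEs).

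| rho | Variance ratio, month 1 / 2 / 3 | Month-3 SE, planned / common | Detectable difference, planned / common |
|---|---|---|---|
| 0.3 | 1.504 / 1.473 / 1.446 | 0.159 / 0.133 | 0.446 / 0.371 |
| 0.5 | 1.312 / 1.290 / 1.272 | 0.137 / 0.121 | 0.383 / 0.340 |
| 0.7 | 1.165 / 1.154 / 1.146 | 0.106 / 0.099 | 0.298 / 0.279 |
| 0.8 | 1.104 / 1.097 / 1.092 | 0.087 / 0.083 | 0.244 / 0.234 |
| 0.9 | 1.049 / 1.046 / 1.044 | 0.062 / 0.060 | 0.173 / 0.169 |

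Where the common-baseline model has 80% power at month 3, the planned contrast has power Φ(2.802/sqrt(ratio) - 1.960), which is 64%, 70%, 74%, 76% and 78% down the table.

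**Sensitivity to the assumptions.**

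- Dropout timing at rho 0.3: the month-3 ratio is 1.43 if all dropout precedes T1 and 1.46 if all follows T2.
- Unequal SDs, same dropout, rho 0.2 to 0.9: 1.00 to 1.26 if s = 0.75, and 2.03 to 2.58 if s = 1.5.
- The 125 at baseline is itself assumed. Section 4.7 counts attrition from enrollment, and under section 4.1.5, when the infant does not meet the criteria at birth, "they are withdrawn from the study and are not randomized".
- If other covariates are added, rho and s become the partial values.

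**Under multiple imputation.** In 3,000 simulated trials per setting (multivariate normal, no treatment effect, dropout completely at random, 20 imputations), the Rubin variance ratio of the month-3 change score to the baseline-adjusted estimate was 1.44, 1.27, 1.14 and 1.09 at rho 0.3, 0.5, 0.7 and 0.8. Type I error was 4.5% to 5.5% for both.

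**Bias.** In 20,000 complete-data simulations at rho 0.5 with a true effect of 0.30, the mean estimates were 0.302 (change) and 0.300 (adjusted).

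**The case against.** The planned contrast is legitimate and pre-specified, and it matches the abstract and synopsis, which compare oxytocin function with the prenatal baseline. No power is claimed for these tests, so no stated figure fails. The size rests entirely on assumed inputs: with s = 0.75 and rho of 0.7 to 0.8 there is practically no loss. The plan is also not closed to adjustment. Section 4.8 lists analysis of covariance, the covariates in 4.8.1 are only examples, and sensitivity analyses are promised for baseline imbalance. Replacing a main contrast late in the trial, after planned preliminary outcome analyses, could look post hoc.

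Much of this stands. It is an efficiency point on secondary outcomes, and the gain cannot be fixed from the documents. But permission to adjust is not a specification, and the imbalance analyses are conditional and leave the main model unchanged. The timing risk is real and is met by dating and justifying the change and still reporting the planned contrast.

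On saliva, the words about a late-pregnancy baseline could be read as excluding infant samples, and both the general Aim 1 goal and H1 supply comparisons that can be estimated. However, Table 2 puts plasma and saliva in one row with a baseline/in-hospital mark, which invites the opposite reading. And if saliva is excluded, it has no clearly assigned model. One clarifying line is needed on either reading.

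**Conclusion.** The concern holds as a matter of precision, not validity. As written, the maternal-marker model estimates a baseline arm difference known to be zero. In large samples it is never more precise than a common-baseline or baseline-adjusted analysis of the same quantity. With equal SDs the loss is material at low to moderate correlation and small from about 0.8. A baseline SD well above the month-3 SD would make it larger; one close to rho times the month-3 SD would remove it. The true loss is unknown and may be small. The saliva gap needs only a clarification. The primary gaze and affect analyses and their 80% power figure are untouched.

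**What to change.** In section 4.8.1:

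1. Fit the maternal-marker MMRM with a common baseline mean (time plus treatment-by-postnatal-time, no treatment term at baseline). Alternatively, model months 1 to 3 with the marker's baseline value, by time, as a covariate.
2. Use the same baseline handling in the multiple-imputation analysis.
3. Report the month-3 arm difference as the main contrast, with the month 1 and 2 differences that H1 names. Keep the planned change contrast as a sensitivity analysis.
4. Add one line: infant salivary oxytocin is exempt from the change contrast and is analysed by the arm difference at T3 (and at T1 and T2 for H1) from an MMRM over T1 to T3.

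The comparison with prenatal baseline in the abstract and synopsis can stay, because the quantity estimated is the same.

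The cost is little code and no new data. Collection was projected to end on 31 March 2024 (section 1.2), and preliminary outcome analyses were planned at the start of years 2 and 3 (section 7.1). The choice should therefore be documented, justified and dated before the final analysis.

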3.0 OBJECTIVES AND ENDPOINTS

3.1 Study Overview

We will test the ATVV, a multisensory behavioral intervention, where mothers learn to engage with their infant while administering Auditory (infant directed speech), Tactile (massage), Visual (eye to eye gaze), and Vestibular (rocking) stimulation.⁽²⁴⁾ We build on ATVV's success with preterm infants and their mothers (e.g., improved maternal sensitivity, lower maternal distress, and enhanced infant behavior and development) to determine benefits for full-term M-I dyads.⁽²⁵⁻³⁰⁾ We will target first-time mothers with childhood adversity. Mothers randomized to ATVV will administer it once daily for the first 3 postnatal months. At 3 months, when full-term infants reliably exhibit clear cues and maintain alertness, we will apply a rigorous behavioral measure of M-I synchrony developed by a member of our team using frame-by-frame video of micro-coded M-I behavior quantifying reciprocal speech, touch, gaze, and affect.^(31, 32, 73) Micro-coded behavior yields rich detail of interaction patterns known to influence long-term developmental outcomes.^(7, 18, 19) Our feasibility pilot showed significant and strong correlations between ATVV frequency and improved M-I synchrony over one month.

We will also assess ATVV's effect on maternal and infant peripheral OXT levels,^(7, 19) a known biomarker of M-I synchrony. We, and others, have shown that dampening in the OXT system (i.e., abnormally low OXT blood and saliva levels) is evident in poor M-I synchrony and maternal behavior,⁽³³⁻³⁷⁾ yet little is known about OXT's epigenetic regulation of synchrony or maternal behavior in humans. Thus, we will target regions of the **OXT receptor gene (OXTR)** where DNA methylation is linked to maternal behavior in rodents, psychosocial behaviors in humans, and in our pilot study to M-I synchrony.⁽³⁸⁻⁵²⁾ We will examine whether our OXT measures emerge early to predict efficacy of ATVV and quality of M-I synchrony at 3 months. We analyze maternal blood in pregnancy and at 1, 2, and 3 months post birth (and infant salivary OXT). We aim to identify molecular mechanisms in the OXT system underlying M-I synchrony in maternal blood and discover molecular profiles. Regression based methods assess ATVV effects on and relations among M-I synchrony and OXT measures.

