3.3.1.4 Categories of Synchrony

Two variables are created as measures of synchrony via conditional probabilities (parent in behavior X while infant in behavior Y). Affect Synchrony: episodes in which parent and infant simultaneously express positive affect. Gaze Synchrony: episodes in which mother and child both look at each other's face. Vocal Synchrony: mother expresses "motherese" vocalization while infant emits positive vocalizations. Touch Synchrony: mother touches infant affectionately when mother and infant share social gaze.

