3.3.1.5 Coding Procedures

At the study session, once the infant is in an alert state, mothers are instructed to freely interact with their infant during 4 minutes of video recording. When coding, the first minute is ignored and coding occurs on the final 3-minutes. Interactions are micro-coded frame by frame on a computerized system (Noldus, Waggenigen, The Netherlands), consistent with previous research on parent-infant synchrony.^(31, 102-103) Coders of the videos are blinded to group condition. They will prepare the videos for coding, code the data, and transfer data into a form ready for analysis. Coders are trained to 90% inter-rater reliability, and 20% of videos will be double coded for inter-rater reliability. Coding of mother-infant synchrony has been validated in multiple studies and measures of synchrony have shown to correlate with maternal and infant risk conditions, oxytocin and cortisol levels, maternal brain response to infant cues, and to predict better social adjustment, cognitive functions, and autonomic regulation in research spanning birth to adolescence.^(7, 19, 63)

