4.3 Intervention Compliance

To monitor mothers' fidelity and dosage of ATVV once daily, we will use text messaging through Twilio, an electronic communications platform within REDCap. To have access to a phone capable of text messaging is an inclusion criterion to participate in the study. Participants may tire of responding to daily texts, but our daily text is extremely brief requiring only a keystroke to respond. If a phone becomes lost, we will provide a temporary one. Each evening, Twilio will text the following-

- Please tell us how many minutes you gave your baby the Massage Plus today. Choose between 0-15 minutes.
- Please tell us the level of stress you may have experienced today on a scale of 0-10.

The question on stress is included because the attention-control mothers also receive the identical text message and stress is a covariate. See section 4.5. We will monitor REDCap daily, and call mothers if we identify noncompliance two days in a row. Second, we will ask during the weekly phone calls if anyone else besides the mother gave the massage. At each weekly phone call and monthly study visit, we will review how often mothers use the intervention (self-report vs REDCap data) and discuss solutions to barriers of fidelity (e.g. lack of time, fussy or sleepy infant). We will also discuss who else may be giving the massage to their baby.

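### The per-protocol rule can screen only the ATVV arm, so if adherence goes with better synchrony the per-protocol contrast favours ATVV even with no effect

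*Combined protocol and SAP*

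**What the plan says.** Section 4.8.1 (Evaluate Efficacy of ATVV) plans ITT, with multiple imputation so that all randomised participants are retained, and "per protocol analyses (defined as completing 80% or more of daily ATVV sessions) and compare our findings". This is the only per-protocol criterion in the document. On exposure data the section says "Dose (frequency of ATVV sessions) will be collected daily for three months from the treatment arm participants".

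Section 4.4 gives controls didactic infant-care education, weekly calls and monthly visits. It sets no threshold for any of these. Section 4.3 notes that "the attention-control mothers also receive the identical text message", but gives the stress question as the reason and does not make the text a compliance criterion for controls.

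Section 4.8.1 does not say how controls enter the per-protocol set, or which analysis decides if ITT and per protocol disagree.

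**The concern.** A session criterion can be met or failed only by mothers who were asked to give sessions. Applied literally to both arms it would remove every control. A usable two-arm comparison must therefore keep the controls and screen the ATVV arm alone on behaviour after randomisation. The groups compared are then no longer the randomised ones.

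The direction of any bias depends on who fails the screen. Section 4.3 says staff will "discuss solutions to barriers of fidelity (e.g. lack of time, fussy or sleepy infant" with the ATVV mothers. One primary outcome is "Affect Synchrony: episodes in which parent and infant simultaneously express positive affect" (section 3.3.1.4). A mother short of time, or with a fussy infant, may both miss sessions and score lower for reasons unrelated to ATVV. Section 3.1 adds "Our feasibility pilot showed significant and strong correlations between ATVV frequency and improved M-I synchrony over one month". A benefit of ATVV would produce that correlation, and so would selection.

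At stake is how the planned comparison is read. A per-protocol difference larger than ITT could be taken as the benefit of ATVV when it is given as intended, although selection alone can produce the same pattern.

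**Working it through.** **The plan's own figure.** Inputs from section 4.7: 250 enrolled, 20% attrition, 0.44 SD, two-sided alpha 0.025, 80% power. 250 × 0.8 = 200, or 100 per arm. The detectable difference is (2.241 + 0.842) × √(2/100) = 0.436 SD, and power at 0.44 SD is 80.8% (normal) or 80.2% (noncentral t). The stated power reproduces. The documents give no figure for the per-protocol set.

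**Simple model of the one-arm screen.** Let there be no ATVV effect. Let a mother's tendency to adhere correlate r with her synchrony, let a share q of ATVV mothers pass, and keep all controls. Then

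bias = r × φ(c)/q SD, where c is the normal quantile at 1 − q.

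- q = 0.8, r = 0.3: 0.3 × 0.280/0.8 = 0.105 SD.
- q = 0.6, r = 0.3: 0.3 × 0.386/0.6 = 0.193 SD.
- r = 0: no bias at any q. A negative r reverses the sign.

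Both q and r are assumptions. If the same screen, with the same q and r, is applied in both arms (q = 0.6, r = 0.3), the simulated bias is 0.00 SD and the two-sided error 2.6%. The one-arm screen gives 0.19 SD and 14.5%. The asymmetry is therefore the cause.

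**Model with daily sessions and texts.** Assumptions: true effect 0, 100 per arm, 84 days (68 needed, since 0.8 × 84 = 67.2), mean completion 90%, mean text response 90%, intraclass correlation 0.10, unadjusted t-test at two-sided 0.025, 20,000 simulated trials. The plan does not say how an unanswered text counts, so three scorings are shown. Each cell gives the bias in SD, then the chance of a false result favouring ATVV on one primary outcome (nominal 1.25%).

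| Unanswered text counted as | ATVV kept | r = 0.1 | r = 0.3 | r = 0.5 |
|---|---|---|---|---|
| missing, at least half answered | 85 | 0.027; 2.0% | 0.077; 4.3% | 0.130; 8.8% |
| no session, half recovered by calls | 74 | 0.038; 2.4% | 0.110; 6.4% | 0.185; 14.8% |
| no session, none recovered | 59 | 0.043; 2.4% | 0.126; 6.9% | 0.211; 16.7% |

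At r = 0 every set has bias 0.00 and a rate of 1.1% to 1.2%. Analysing all 100 mothers per arm, as ITT does, gives bias 0.00 and 1.2% to 1.3% throughout.

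**Mean completion varied (r = 0.3, 90% response).** At 95% completion the bias is 0.035 to 0.07 SD across the three scorings. At 80% it is 0.195 to 0.26 SD. Against the 0.44 SD design difference, the 90% case is 0.077/0.44 = 18% to 0.126/0.44 = 29%. The full range is 0.035/0.44 = 8% to 0.26/0.44 = 59%.

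**The case against.** The strongest reply is that ITT is listed first, carries the imputation plan and is untouched, while no claim is attached to per protocol beyond a comparison. This stands, and it limits the matter to a supporting analysis. It does not make that comparison informative.

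Section 4.8.1 also plans adjusted estimates, with covariates that include mental health, infant health status and the one-month Parenting Stress Index. These may capture part of what drives adherence, and the figures above ignore them. However, available time is not among the covariates named there, and the per-protocol analysis is not tied to the adjusted models.

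The link between adherence and prognosis is an inference. Section 4.3 lists barriers without relating them to synchrony, and the pilot correlation has no figure. Filming starts only "once the infant is in an alert state, mothers are instructed to freely interact with their infant", which weakens the route through a fussy or sleepy infant. A reader might infer that the rule favours ATVV whatever the circumstances, or that the protocol itself shows adherence to be prognostic. The documents support neither: the bias is zero at r = 0, would reverse at negative r, and keeping every control is the workable reading rather than a stated rule.

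Nor should non-response be assumed to be heavy. Section 4.3 says "Participants may tire of responding to daily texts", but goes on to stress how short the text is, and staff check replies daily and call after two days of noncompliance. The scoring of silence changes the size of the bias and is not its source.

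**Conclusion.** The concern holds in conditional form. The only per-protocol criterion can act on the ATVV arm alone, so a workable per-protocol contrast is not a randomised comparison. It favours ATVV under no effect if adherence is positively related to synchrony apart from any ATVV effect.

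With r = 0.3 assumed, 100 per arm and no adjustment, the spurious gain is 0.08 to 0.13 SD at 90% completion, with a one-sided false-positive rate of about 4% to 7% against 1.25%. Across 80% to 95% completion it is about 0.03 to 0.26 SD. At r = 0.1 and 90% completion it is small (0.03 to 0.04 SD). None of r, completion or text response is given in the documents. A reader might infer that the trial's efficacy result is biased; it is not, because ITT keeps both randomised groups whole.

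**What to change.** Amend section 4.8.1 before outcomes are analysed:

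1. State that ITT decides both primary outcomes and that per protocol cannot override it.
2. Replace the one-arm contrast as the inferential adherence analysis with an instrumental-variable estimate that uses randomised arm as the instrument. In the dose-scaled form this is the ITT difference divided by the mean share of session-days in the ATVV arm, with controls at zero. At 90% completion that is ITT × 1/0.90 = ITT × 1.11. Its test is in effect the ITT test, so selection on adherence cannot create a positive result. A complier version is the alternative.
3. If the 80% set is kept, report it as descriptive with no significance claim, and tabulate baseline characteristics of included and excluded ATVV mothers.

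A parallel control criterion, such as a share of weekly calls completed, is a weaker remedy. It removes the bias only if it selects on prognosis to the same degree as the session rule, which cannot be checked.

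The cost is SAP wording and one extra model on data already planned. The downside is the model's assumptions: that assignment acts only through sessions given, that controls give no ATVV and, for the dose-scaled form, that benefit is proportional to sessions.
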